6.6 Characterisation of selected comorbidity clusters (phase 2)

The associations between the individual diseases in the selected clusters will be illustrated in graph format (appendix 11). This will show which diseases are often diagnosed together. An edgelist, a list of all disease pairs in the clusters, will be used to calculate the position of each disease in two-dimensional space using a multidimensional scaling procedure.

This will include an investigation of the characteristics of each cluster by comorbidity severity and activity, eosinophil count and age. Patient demography and asthma severity will also be compared within and between these key comorbidity clusters. Associations between specific co-morbidity patterns and disease severity will be estimated using logistic regression, adjusting for confounders.

The list of tables and figures to be produced will be finalised at the beginning of phase 2.

6.7 Healthcare resource utilisation (HRU) and costs (phase 2)

The HRU outcomes and associated costs will be calculated and reported for each of the outcomes of interest in the year prior to the index date (mock table in appendix 12).

Associations between specific co-morbidity patterns and healthcare resource utilisation and costs will be estimated using generalised estimating equations with cluster robust standard errors, log link and gamma distribution, adjusting for confounders.

Secondary care resource use and costs will be limited to patients whose practices have linked secondary care (HES) data.

Prices assigned to primary care consultation costs will be taken from the latest Personal Social Services Research Unit (PSSRU) document (<http://www.pssru.ac.uk/project-pages/unit-costs/2017/index.php>)

Prices assigned to secondary care costs will be based on the national average hospital costs as found in PSSRU document.

Prices assigned to drugs will be taken from the Dictionary of Medicines and Devices browser (<http://dmd.medicines.org.uk/>). The electronic British National Formulary (eBNF) and the Medical Index of Medicinal Substances (MIMS) will be used to fill any gaps.

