4.2 Inclusion and exclusion criteria

Inclusion criteria

Registered at a participating practice for at least one year prior to their index date and within the study period. In phase 1, the cross-sectional assessment of co-morbidity co-occurrence, the index date for each patient will be the earlier of the following dates: the last data collection from each practice and 6 months before patient deregistration (to avoid gaps in the clinical data due to late recording of patient deregistrations). For CPRD practices with linked HES data, the index date will be the earliest of the following dates: the last data collection from each practice, 6 months before patient deregistration, date of last HES record. In phase 2, the index date will be one year before the last data collection from each practice and 6 months before patient deregistration, to allow for one year of follow-up.

Patient had active asthma at their index date:

- a diagnosis of asthma at any time before their index date (using QOF Read codes: see Appendix 1); AND
- two or more prescriptions for an asthma medication in the preceding year.

Exclusion criteria

Any other chronic lower respiratory condition recorded at any time (Read coded: see Appendix 2). These are:

- Lung disease due to external agents, other than smoking, such as occupational agents.
- Active COPD (a Read code at any time + medication in the last year of follow-up).
- Bronchiolitis obliterans.
- Pulmonary fibrosis.
- Pulmonary hypertension.
- Cystic fibrosis

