5.4 Quantifying health resource use (HRU) and costs

The following HRU outcomes and associated costs will be tabulated for each of the comorbidity clusters identified in phase 1. These will be for the year prior to the index date. Secondary care resource use and costs will be limited to patients with linked secondary care (HES) data and the most recent HES year. Costs will be reported in 2017 GB pounds.

Primary care

1. Physician office visits:
 - a. Number and cost of asthma-related consultations.
2. Number of primary care medication prescriptions:
 - a. ICS
 - b. ICS/LABA
 - c. SABA
 - d. SAMA
 - e. LABA
 - f. LAMA
 - g. LABA/LAMA
 - h. LTRA
 - i. biologics (where known)
 - j. chronic oral corticosteroids
 - k. antibiotics
3. Total cost of asthma drug prescribing.
4. Total cost of oral corticosteroid and antibiotic prescribing.
5. Total primary care costs (physician office visits + prescribing).

Secondary care

6. Outpatient visits:
 - a. Number and cost of asthma-related outpatient visits.
7. Emergency Room attendances:
 - a. Number and cost of asthma-related Emergency Room attendances.
8. Inpatient hospital admissions:
 - a. Number and cost of asthma-related hospital admissions.
9. Total secondary care costs (outpatient + ER + inpatient).

Combined primary and secondary HRU and costs

11. Total primary and secondary care costs (primary care + secondary care).

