6.8 Confounding handling approach

The multivariable models will be adjusted on variables that are known or show to confound the association of interest. For this we will use both expert opinion and a data driven technique using bias potential.

Expert opinion will decide what set of baseline characteristics will always be adjusted on in the models. Also, expert opinion will decide on the set of candidate confounders to consider in the next step, using bias potential assessment. This assesses the degree to which the observed association between the exposure of interest and the outcome is affected by conditioning on the variable. It measures the relative change in coefficient of the exposure compared to the model without the candidate confounder. Confounder candidates will be introduced into the model iteratively, the one with the highest bias potential first. If the observed change in estimate is more than 2%, the variable is kept in the model, and all remaining candidates are re-evaluated until none of the confounder candidates are left or none cause a change in estimate of more than 2%.

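### Phase 2 fits one gamma model to utilisation counts as well as costs, and states cluster-robust errors for that model but not for the logistic severity models

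*Protocol*

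**What the plan says.** - **Utilisation and costs (Protocol 6.7).** The method named is "generalised estimating equations with cluster robust standard errors, log link and gamma distribution, adjusting for confounders". This one model specification serves both the utilisation and the cost outcomes. The unit that defines a cluster is not named.
- **The outcomes (Protocol 5.4).** The list includes "Number and cost of asthma-related hospital admissions" and "Number and cost of asthma-related Emergency Room attendances", together with numbers of consultations, outpatient visits and prescriptions. These are counts per patient over one year, each paired with a cost.
- **Severity (Protocol 6.6).** "Associations between specific co-morbidity patterns and disease severity will be estimated using logistic regression, adjusting for confounders". Nothing is said about correlation within practices or about robust errors.
- **Covariates (Protocol 6.8).** An expert-chosen set is always adjusted for. Further candidates enter by a change-in-estimate rule, whose metric is described as follows: "It measures the relative change in coefficient of the exposure compared to the model without the candidate confounder". The cut-off is fixed separately: "If the observed change in estimate is more than 2%, the variable is kept in the model".
- **Eligibility (Protocol 4.2).** Active asthma requires "two or more prescriptions for an asthma medication in the preceding year".

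**The concern.** A gamma model treats the variance as proportional to the squared mean. That suits skewed positive costs. It does not suit rare integer counts, whose variance is close to the mean. The gamma fit then gives too much weight to residuals from patients with a very low expected count, and the estimate becomes noisier than it need be. At stake is the precision of the comparisons on admissions and ER attendances.

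The second issue is a mismatch between two neighbouring sections. The patients come from the same practices in both. The comorbidities are identified from Read codes (5.2), and GINA step comes from prescribed medication (5.1). Both could vary by practice. Section 6.7 allows for clustering and 6.6 does not mention it. If the severity models are run as 6.6 reads, their confidence intervals are likely to be too narrow. The reader also cannot be sure what the robust errors in 6.7 are clustered on, because elsewhere in the protocol a cluster is a combination of comorbidities.

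**Working it through.** The protocol gives no event rate, share of zeros, ICC, alpha or power, so there is no figure of its own to reproduce. Shares of zeros and ICCs below are assumptions.

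**1. Gamma against Poisson for counts**

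With a log link, each patient contributes x(y − μ)·μ/V(μ) to the estimating equation.
- Poisson, V = μ: contribution x(y − μ).
- Gamma, V = μ²: contribution x(y − μ)/μ.

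Both have expectation zero if the mean model is right, so zeros do not bias the gamma fit. For rare counts the true variance is near μ, so the Poisson weights are close to optimal and the gamma weights are not.

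Simulation: 150 runs of 100 practices × 100 patients, overdispersed counts, true log rate ratio 0.2, one confounder, practice-robust errors for both fits.

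| Zeros | Confounder | Empirical SD, gamma | Empirical SD, Poisson | Variance ratio | Gamma coverage |
|---|---|---|---|---|---|
| 96.6% | moderate | 0.1651 | 0.1505 | 1.20 | 94.7% |
| 89.6% | moderate | 0.0896 | 0.0800 | 1.25 | 95.3% |
| 87.1% | stronger | 0.0984 | 0.0734 | 1.80 | 94.0% |
| 49.4% | moderate | 0.0427 | 0.0433 | 0.97 | 92.7% |
| 49.5% | stronger | 0.0389 | 0.0496 | 0.62 | 98.0% |

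Mean gamma estimates were 0.19 to 0.21. A sixth setting (95.4% zeros, stronger confounder) gave a ratio of about 21 and 78% coverage. That probably reflects non-convergence in part, so it is not used for sizing.

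A ratio of 1.2 to 1.8 widens intervals by √1.2 = 1.10 to √1.8 = 1.34.

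**2. Clustering in the logistic models**

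Patients per practice, from sections 4.1 and 6.1:
- OPCRD: 220,000/700 = 314.
- HES-linked CPRD: 260,000/300 = 867.

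For a patient-level exposure, the design effect is 1 + (m − 1) × ICC(exposure) × ICC(outcome). The SE factor is its square root. True coverage of a nominal 95% interval is 2Φ(1.96/SE factor) − 1.

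| m | Both ICCs | Design effect | SE factor | Coverage |
|---|---|---|---|---|
| 314 | 0.01 | 1 + 313 × 0.0001 = 1.031 | 1.016 | 94.6% |
| 314 | 0.02 | 1 + 313 × 0.0004 = 1.125 | 1.061 | 93.5% |
| 314 | 0.05 | 1 + 313 × 0.0025 = 1.783 | 1.335 | 85.8% |
| 867 | 0.01 | 1 + 866 × 0.0001 = 1.087 | 1.042 | 94.0% |
| 867 | 0.02 | 1 + 866 × 0.0004 = 1.346 | 1.160 | 90.9% |
| 867 | 0.05 | 1 + 866 × 0.0025 = 3.165 | 1.779 | 72.9% |

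**3. The 2% rule**

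The cut-off on the log-odds scale is 0.02 × ln(OR).
- OR 1.02: 0.02 × 0.0198 = 0.0004.
- OR 2.0: 0.02 × 0.693 = 0.0139, about 35 times larger.

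The rule is therefore hypersensitive near a null effect. At any effect size, however, a single candidate left out at the final step moves the coefficient by no more than 2%. At OR 2.0 that is a move to 2^1.02 = 2.03.

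**The case against.** **Gamma.** A GEE needs a mean model and a working variance, not a gamma likelihood, so it is no error that the gamma distribution has no mass at zero. This stands. A reader might infer biased or invalid estimates, and neither the theory nor the simulations support that outside the one extreme setting.

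Nor are all the outcomes mostly zero. On the year before index, which 5.4 and 6.7 use, the eligibility rule guarantees at least two asthma prescriptions, so total asthma prescribing and its cost cannot be mostly zero. The point reaches only rarer outcomes such as admissions and ER attendances. Larger losses can be produced: with no overdispersion and a log-mean SD of s, the variance ratio is exp(s²), or 2.72 at s = 1. The documents give no basis for choosing such inputs.

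**Clustering.** Section 6.6 is silent; it does not claim independence. Variance estimation is often left to a SAP, which is not available here. This also stands, so the point rests on the contrast with 6.7 and the unnamed unit, not on omission alone. The practical effect may be small. Take 220,000 patients, 85,000/220,000 = 39% at GINA steps 4 and 5, and an assumed 5% exposure with OR 1.3. The SE of the log OR is √[1/(11,000 × 0.247) + 1/(209,000 × 0.236)] = 0.0197, which gives an interval of 1.25 to 1.35. Inflated by 1.335, it is 1.23 to 1.37.

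**The 2% rule.** A reader might infer that the rule leaves each comorbidity cluster adjusted differently, so that clusters cannot be compared. The protocol does not say that selection runs separately for each cluster and outcome, and the always-adjusted set limits any difference. Odds ratios do shift when a purely prognostic covariate enters, but a fixed set containing that covariate would shift them equally.

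**Conclusion.** The point holds in a limited form.

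- **Count outcomes.** The gamma working variance is a poor choice for rare utilisation counts. The cost is precision, not validity: about 1.2 to 1.8 times the Poisson variance at roughly 87 to 97% zeros, and none at about 50%. The share of zeros is an assumption, plausible for admissions and ER attendances only.
- **Severity models.** Sections 6.6 and 6.7 are inconsistent on clustering, and the unit is not named. If 6.6 is run without robust errors, the correct SE is 1.02 to 1.34 times the naive one at 314 patients per practice, and 1.04 to 1.78 times at 867. This assumes ICCs of 0.01 to 0.05 for both exposure and outcome. The direction is certain only if both ICCs are positive; the upper figures need both at 0.05.
- **Covariate rule.** Its relative scale is unstable near a null effect. The documents do not show that it makes comorbidity clusters non-comparable.

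**What to change.** 1. In 6.7, separate the outcomes. Use a log-link Poisson or negative binomial GEE for utilisation counts. No follow-up offset is needed while every patient contributes a full year. Keep the log-link gamma for costs that are positive for nearly all patients. For secondary care costs with many zeros, a two-part model (any cost, then cost if positive) is an option.
2. Name the general practice as the clustering unit, and state practice-robust errors for all Phase 2 models, including the logistic models in 6.6. Robust errors clustered on the small set of selected comorbidity clusters would have too few units to be reliable, so the wording should exclude that reading.
3. Optional: use one pre-specified adjustment set for all comorbidity clusters, and keep the relative-change rule as a sensitivity analysis.

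The cost is a few lines of code before Phase 2 and somewhat wider confidence intervals for the severity odds ratios. No extra data are needed.

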6.8 Confounding handling approach

The multivariable models will be adjusted on variables that are known or show to confound the association of interest. For this we will use both expert opinion and a data driven technique using bias potential.

Expert opinion will decide what set of baseline characteristics will always be adjusted on in the models. Also, expert opinion will decide on the set of candidate confounders to consider in the next step, using bias potential assessment. This assesses the degree to which the observed association between the exposure of interest and the outcome is affected by conditioning on the variable. It measures the relative change in coefficient of the exposure compared to the model without the candidate confounder. Confounder candidates will be introduced into the model iteratively, the one with the highest bias potential first. If the observed change in estimate is more than 2%, the variable is kept in the model, and all remaining candidates are re-evaluated until none of the confounder candidates are left or none cause a change in estimate of more than 2%.

6.9 Sensitivity analyses

It can be expected that the observed prevalence of a co-morbidity is partly a function of the distribution of the length of the available medical record data, which can vary considerably. We assume that when a patient moves from one GP practice to another, the most relevant morbidity information remains available in the medical record. To assess to what extent our assumption holds, we will repeat the phase 2 analyses in a subset of patients for whom we have at least 5 years of medical record history available.

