2.2 Study objectives

Phase 1: The primary objective is to estimate the frequency of each combination/cluster of T2 type comorbidities in a real world active asthma population, and to select, by consensus, a limited set of common comorbidity clusters for further investigation.

Phase 2: The primary objective is to describe the overlap between these clusters and between individual comorbidities within the clusters in terms of patient demography, and asthma severity, resource utilisation and costs.

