5.2 Identifying comorbidities of interest

The nine T2-type comorbidities of interest (atopic dermatitis; allergic rhinitis; chronic rhinosinusitis; nasal polyps; urticaria; allergic conjunctivitis; food allergy; eosinophilic oesophagitis; and anaphylaxis) will be identified by the presence of a Read code for the condition in the patient record. Anaphylaxis will also be identified by the prescription of adrenaline. Appendix 3 lists conditions where there are existing Read code definitions and those which will be developed during the study.

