6.5 Identification and selection of comorbidity clusters (phase 1)

There are over 500 possible combinations of the 9 comorbidities of interest. The prevalence of each combination of comorbidities will be tabulated (including patients with no comorbidities) (see mock table in appendix 8). Clusters will be ranked by prevalence. The ratio of observed cases to expected for each cluster and cumulative proportion of population accounted for at each step will be calculated.

Visualisations of the frequency and age distribution of comorbidity in the asthma population will be produced. A table with the source data will accompany each figure. The first figure will chart the frequency of comorbidities in the study population (see illustrative example in appendix 9). The second figure will chart the mean number of comorbidities in the asthma population by age group and gender (appendix 10).

A small set of key comorbidity clusters will then be selected by consensus for further analysis in phase 2. This will be based on their clinical importance, prevalence, observed/expected ratio and cumulative proportion of population included.

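### The only check on unequal record length is assigned to Phase 2, after the Phase 1 prevalences and observed/expected ratios have already been used to choose the clusters

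*Protocol*

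**What the plan says.** Section 6.9 is the protocol's only sensitivity section. It states that "the observed prevalence of a co-morbidity is partly a function of the distribution of the length of the available medical record data". It assumes that the relevant history follows a patient who changes practice, and it tests that assumption in one way: "we will repeat the phase 2 analyses in a subset of patients for whom we have at least 5 years" of record.

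The Phase 1 objective in section 2.2 reads: "The primary objective is to estimate the frequency of each combination/cluster of T2 type comorbidities in a real world active asthma population". Section 6.5 tabulates and ranks all combinations of the nine diseases, with their observed/expected ratios. The clusters are then chosen by consensus, "based on their clinical importance, prevalence, observed/expected ratio and cumulative proportion of population included".

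Three other provisions decide how record length enters these figures:

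- Section 4.2, entry: "Registered at a participating practice for at least one year prior to their index date and within the study period".
- Section 5.2, ascertainment: the diseases "will be identified by the presence of a Read code for the condition in the patient record". No fixed look-back window is given. Anaphylaxis can also be identified by an adrenaline prescription.
- Section 6.4, expected prevalence: the single-disease prevalences are multiplied together, with no stratification by record length.

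The timeline in section 11.0 lists the Phase 1 analyses, then the sponsor's sign-off on the clusters, then the CPRD data and the Phase 2 analyses.

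**The concern.** The quantity that section 6.9 worries about is prevalence. Prevalence is the Phase 1 primary output and a named criterion for choosing clusters. Two of the other three criteria, the observed/expected ratio and the cumulative proportion, are built from the same counts. A repeat of the Phase 2 analyses describes clusters that are already fixed. It comes too late to show whether a different set would have been chosen had every patient had a reasonably long record.

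The observed/expected ratio is exposed in a particular way. If a longer record makes every disease more likely to be coded, patients with long records tend to carry several codes and patients with short records few. Multiplying overall prevalences ignores this, so some apparent association can come from record length alone. What is at stake is the ranking put before the consensus group, and hence what Phase 2 studies.

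**Working it through.** **1. Order of steps.** Prevalence, rank and ratio are produced in Phase 1 (6.5). Clusters are selected from them (6.5) and signed off (11.0). The Phase 2 analyses follow, and the 5-year repeat belongs to those (6.9). This ordering comes from the text alone and needs no calculation.

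**2. Direction and size: two groups of patients.** The protocol gives neither a distribution of record length nor capture rates, so every input here is an assumption. A share w of patients has short records. A truly present disease is coded with probability s in short records and L in long ones. The diseases are independent. For patients with at least k given diseases:

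- spurious ratio = [w·s^k + (1−w)·L^k] / [w·s + (1−w)·L]^k
- prevalence relative to long records = [w·s^k + (1−w)·L^k] / L^k

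| w, s, L | Ratio, k = 2 / 3 / 4 | Relative prevalence, k = 2 / 3 / 4 |
|---|---|---|
| 0.2, 0.8, 1.0 | 1.01 / 1.02 / 1.04 | 0.93 / 0.90 / 0.88 |
| 0.3, 0.4, 0.9 | 1.09 / 1.26 / 1.48 | 0.76 / 0.73 / 0.71 |
| 0.5, 0.3, 0.9 | 1.25 / 1.75 / 2.56 | 0.56 / 0.52 / 0.51 |

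Example, second row, k = 2: (0.3·0.16 + 0.7·0.81) / 0.75² = 0.615 / 0.5625 = 1.09.

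**3. Continuous record length.** Let T be uniform on 1 to 20 years, with codes accruing at a constant low rate. The ratio is E[T^k] / E[T]^k, with E[T] = 10.5, E[T²] = 140.33, E[T³] = 2105.25 and E[T⁴] = 33684.2:

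- k = 2: 140.33 / 110.25 = 1.27
- k = 3: 2105.25 / 1157.63 = 1.82
- k = 4: 33684.2 / 12155.06 = 2.77

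This is the rare-disease limit. With coding probability 1 − exp(−λT) and λ from 0.005 to 0.02 per year, the ratios are 1.23–1.26, 1.69–1.78 and 2.45–2.68. At λ = 0.05 they are 1.19, 1.54 and 2.09. With T uniform on 5 to 20 years, the limit falls to 1.12, 1.36 and 1.75.

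**4. Mutually exclusive combinations.** Section 6.5 and the mock table in Appendix 8 point to exclusive rows: over 500 combinations (2⁹ = 512, including none) and a cumulative percentage reaching 100%. The expected value is still the bare product. For nine diseases at a common rate λ and T uniform on 1 to 20, the ratio is E[(1−e^(−λT))^k · e^(−λT(9−k))] / p^k, where p = E[1−e^(−λT)]:

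- λ = 0.005: 0.76 / 1.11 / 1.78
- λ = 0.01: 0.46 / 0.69 / 1.15
- λ = 0.02: 0.19 / 0.28 / 0.50

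Most of these are below 1, because the product leaves out the factor for the absent diseases. Part of the rise with k has the same cause. If every patient had the same capture probability p, the ratio would be (1−p)^(9−k). At λ = 0.005 (p = 0.051) that is 0.69 / 0.73 / 0.77, so the four-disease ratio is 1.11 times the two-disease ratio, against 2.35 times when record length varies. At λ = 0.02 (p = 0.185) the multiples are 1.50 and 2.67. Over these rates, varying record length favours larger clusters relative to smaller ones. At λ = 0.05 for all nine diseases it no longer does (2.65 against 2.19), so the direction is also conditional on the diseases not all being common.

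**The case against.** **Phase 2 repeats the tables.** Section 6.4 covers both phases and plans comparable output in the second, so the 5-year repeat may show shifts in prevalence and ratio. That is a fair reading. Those tables would still arrive after sign-off, and nothing says what would follow from them.

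**The Phase 2 check has its own purpose.** Short records also misclassify cluster membership in Phase 2, so the planned repeat is useful. This stands. The point is that it is not sufficient.

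**History may survive a practice move.** If section 6.9's assumption largely holds, the effect is small, as in the first row of the two-group table: 1–4% on the ratio and 7–12% on cluster prevalence. The protocol does not show whether it holds. Testing that is the purpose of the check.

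**Selection is a judgement.** Clinical importance also counts, and no ratio cut-off is set. This stands, and it limits how far a shifted ratio would change the choice.

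**Stronger readings that the documents do not support.** A reader might infer that independent diseases will generally look clustered in the planned table. For exclusive combinations most null ratios above are below 1. A reader might take the ratio of 2 in the caption under Appendix 11 as this study's threshold. It belongs to a published figure reproduced as a mock example. A reader might conclude that the clusters cannot be changed once Phase 2 starts. The protocol does not say so. It only states no step for revisiting them.

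**Conclusion.** The concern holds as a matter of placement. Section 6.9 names a bias in prevalence and assigns its only check to the phase after prevalence has been used for selection. This conclusion rests on the text and on no assumption about size.

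The size cannot be fixed from the protocol. For patients with at least k independent diseases, the illustrations span about 1.01/1.02/1.04 to about 1.27/1.82/2.77 for 2/3/4 diseases. They assume independence, coding that depends only on record length, and the stated capture rates or uniform record length. They do not carry over directly to exclusive combinations. There, what remains is a relative advantage for larger clusters at low to moderate coding rates, not a ratio reliably above 1. Whether any cluster choice would change is unknown.

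**What to change.** In section 6.9, add that the Phase 1 table of prevalence, rank and observed/expected ratio will also be produced in patients with at least 5 years of record, or stratified by record length, before the consensus selection. Show the full-set and restricted rankings side by side to those making the choice. Keep the Phase 2 repeat.

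The restriction reduces the effect without removing it: in the uniform illustration, triads go from 1.82 to 1.36. The restricted table should therefore be read as a test of how stable the ranking is, not as a corrected result.

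The cost is one extra table from OPCRD data that Phase 1 already uses. The subset excludes the youngest children and recent registrants, so it should stand beside the full set and not replace it.

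### The 5-year restriction in section 6.9 is only a partial check of whether morbidity records survive a change of practice: record history is undefined, movers are not separated, and age is not controlled

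*Protocol*

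**What the plan says.** Protocol section 6.9 starts from the expectation that "the observed prevalence of a co-morbidity is partly a function of the distribution of the length of the available medical record data". It then states the assumption at issue: "We assume that when a patient moves from one GP practice to another, the most relevant morbidity information remains available in the medical record". The purpose of the analysis is tied to that assumption ("To assess to what extent our assumption holds"), and the method is one sentence: the phase 2 analyses are repeated in a "subset of patients for whom we have at least 5 years of medical record history available".

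The section does not say whether history brought in from an earlier practice counts, to which date the 5 years run, or what the result is compared with. It does not identify patients who moved.

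Three other places bear on it:
- Section 4.2 requires a patient to be "Registered at a participating practice for at least one year prior to their index date" and sets no age limit. Appendix 4 has separate GINA step entries for children.
- Section 5.2 finds a comorbidity from a Read code in the record and states no look-back limit. Anaphylaxis can also be found from an adrenaline prescription.
- Section 6.4 gives phase 2 a set of outputs similar to phase 1, so comorbidity prevalence is among the results to be repeated.

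**The concern.** The assumption is about moving, but the check selects on record length, and the two are only loosely linked. A patient whose codes were lost on moving is counted as free of the comorbidity and is placed in the wrong cluster. The phase 2 models for severity, resource use and cost (sections 6.6 and 6.7) rest on those clusters, and this is the only sensitivity analysis that the protocol states.

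As written, neither outcome of the check can be attributed to record transfer. Agreement with the main result could arise because movers with incomplete codes sit in both populations. Disagreement could arise because the subset is older or has been observed for longer. The study could then report that its assumption holds, or fails, on evidence that does not bear on it.

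**Working it through.** Section 6.9 gives no figure to reproduce. All shares and prevalences below are assumptions, because the protocol gives none. The implied comparator is the full phase 2 population, which contains the subset.

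**Step 1: overlap.** Let f be the subset's share of the whole. Then

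subset − whole = (1 − f) × (subset − complement).

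The planned contrast is therefore 70% of the contrast between separate groups at f = 0.3, 50% at f = 0.5, 20% at f = 0.8 and 10% at f = 0.9. It is diluted, but not zero.

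**Step 2: meaning of history.** Assume a true prevalence of 30% in everyone. A share m moved within the last 5 years, and movers keep a fraction r of their coded morbidity. Everyone else has at least 5 years at the practice. The whole population then shows 30% × (1 − m + m·r), and the direct contrast of movers with non-movers is 30% × (r − 1).

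| m | r | Whole | Subset − whole, transferred history counts and codes partly lost | Subset − whole, current practice only | Movers − non-movers |
|---|---|---|---|---|---|
| 0.2 | 0.8 | 28.8% | 0.0 | 1.2 | −6.0 |
| 0.4 | 0.8 | 27.6% | 0.0 | 2.4 | −6.0 |
| 0.2 | 0.5 | 27.0% | 0.0 | 3.0 | −15.0 |
| 0.4 | 0.5 | 24.0% | 0.0 | 6.0 | −15.0 |

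Differences are in percentage points. The zeros arise because movers whose record still spans 5 years stay in the subset with their codes missing. If transferred history counts but loss is all-or-none, movers with lost records fall out, and the contrasts equal those in the current-practice column.

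**Step 3: the same point as ratios, current-practice reading only.** Assume 20% prevalence in patients with at least 5 years at the practice.
- 20% short-registered, half of codes lost: 0.8 × 20% + 0.2 × 10% = 18.0%; 18.0/20 = 0.90, direct ratio 0.50.
- 30% short-registered, half lost: 0.7 × 20% + 0.3 × 10% = 17.0%; ratio 0.85, direct 0.50.
- 20% short-registered, 30% lost: 0.8 × 20% + 0.2 × 14% = 18.8%; ratio 0.94, direct 0.70.

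**Step 4: age.** If the 5 years run to the index date, no child under 5 at index can qualify. Suppose no records are lost at all, prevalence is 30% from age 5, and under-5s are a share s with prevalence p. Then subset − whole = s × (30% − p).
- p = 45%: −0.3 points at s = 2%, −1.5 at s = 10%.
- p = 20%: +0.2 points at s = 2%, +1.0 at s = 10%.

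The upper end is close to the 1.2 points that a modest real loss of codes gives in step 2.

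**The case against.** The strongest reply is that this is an ordinary restriction analysis and does what such an analysis should. If patients with lost records fall out of the subset, comparing it with the whole shows how far the losses move the reported estimates. In step 3, 18% against 20% is the bias in the full-population prevalence; the 0.50 is the loss among short-registered patients and is not the bias in any planned estimate. With about 220,000 OPCRD and 440,000 CPRD patients (section 6.1), a ratio of 0.90 would not be hidden by sampling noise. That stands. Overlap is not an error in itself, and the restriction deserves to be kept.

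It is also fair to say that a statistical analysis plan might define history and its end date. A reader might infer that the protocol counts transferred history and that the check therefore cannot test its assumption. The protocol does not say so: the term is open, and if it means time at the current practice, the check carries real information.

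A reader might likewise infer that every child under 5 is lost. That follows only if history is counted to the index date. Counted to the end of the one-year follow-up, a child aged 4 at index could qualify. The share of under-5s is not given, some of the youngest are already excluded by the one-year registration rule, and the phase 2 models may adjust for age (section 6.8). The age problem therefore bears mainly on prevalence and other unadjusted results.

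What the reply does not meet is the purpose that section 6.9 sets itself. Under no reading does the plan compare movers, or recently registered patients, with others.

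**Conclusion.** The concern holds in a limited form. Section 6.9 sets out to assess survival of records across a change of practice, and the stated method bears on that only indirectly. With transferred history counted and codes partly lost, the check can show 0.0 points while movers lack half their codes. With time at the current practice, it shows 1.2 to 6.0 points where a direct contrast shows 6.0 to 15.0, and age alone can add −1.5 to +1.0 points. These sizes rest wholly on the assumed prevalences, mover shares, code retention and under-5 shares. The ratios of 0.85 to 0.94 are illustrations that apply to the current-practice reading only.

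The documents do not support saying that the check is worthless, or that overlap with the whole invalidates it. It keeps its use for the section's other worry, that prevalence depends on record length. No main estimate changes. This is a cheap improvement to a secondary check that could otherwise give false reassurance or a false alarm.

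**What to change.** In section 6.9:
1. Define history as the time from registration at the current practice to the index date.
2. Keep the 5-year restriction, described as a check on the overall estimates.
3. Add a direct comparison of patients registered under 5 years with those registered at least 5 years, for comorbidity prevalence and the main phase 2 associations. Place patients registered since birth or early infancy in the long group, so that young children with complete records are not lost. Standardise or adjust for age and sex.
4. Report the comparison as an indirect check.

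The cost is a few lines of protocol text, one regrouping and one extra set of results. Registration dates are already needed for the one-year inclusion rule. There are two limits to state. Recent movers may differ from other patients in ways that age and sex do not capture. Some patients in the long group also moved earlier and may have lost codes then, which pulls the contrast towards no difference.
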